All procedures will be carried out by an interventional radiologist at the Regina General Hospital. Confirmation of LPHS diagnosis and eligibility screening will be done by the Principal Investigator a nephrologist at Regina General Hospital. Recruitment will then be conducted by a Nurse Practitioner based on the eligibility criteria, in conjunction with the Principal Investigator. Baseline and follow-up data collection will be done by Nurse Practitioner involved in the study. This clinical team is already well trained in this procedure and have already published a case-study report on the topic in addition to the pre/post cohort study, which was presented at an international medical conference and published ^{15,16}Research Scientist involve in the study will conduct the feasibility measure assessments, data entry, analysis and knowledge translation support. In-kind research support from Research and performance support will provide coordination and analysis services throughout the duration of the study.

Strengths/Weaknesses

Strengths

Our study is a blinded, randomized controlled, crossover feasibility trial which will remove much potential bias that may affect the perceived effectiveness of RDN on LPHS patients. We will be measuring patient outcomes at three different time points, up to six months post intervention, so we may find how patient self-reported pain and quality of life may change over time following the procedure.

Weaknesses

Patients will be followed for up to 6 months following treatments, so we will not be able to discern treatment effectiveness long-term in LPHS patients.

Progress and clinical experience

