Protocol

Feasibility study of a randomised controlled trial investigating renal denervation as a possible treatment option in patients with Loin Pain Hematuria Syndrome

Overview

Loin Pain Hematuria Syndrome (LPHS) is a rare and poorly understood clinical condition characterized by severe, unilateral or bilateral loin pain localized to the kidney in the absence of identifiable urinary tract disease. The presence of pain-carrying fibers in the renal arterial adventitia presents an opportunity to interrupt the pathways by using radiofrequency nerve ablation as an alternative to chronic pain medication. Recent case reports and small case series from our group and others have shown renal denervation to be a potent therapeutic target for patients with LPHS.

The present study is a prospective, double-blinded, parallel group, sham-controlled, partial crossover, randomized feasibility trial. This feasibility trial is designed with an aim to determine the viability of the proposed main trial initiative and to provide framework and direction for the larger randomized control trial. This study is intended to supplement a larger clinical trial to assess both statistical and clinical significance of renal denervation treatment in LPHS patients. Renal denervation will be performed using the Symplicity SpyralTM multi electrode renal denervation system - a percutaneous system that delivers radiofrequency (RF) energy through the luminal surface of the renal artery. This study will enrol 10 LPHS patients and will be conducted at a single site i.e. Regina General Hospital.

Study Hypothesis: In the present study we hypothesise that the recruitment, intervention, measurement and trial procedures will be feasible and acceptable, thus allowing us to proceed with a full randomised control trial

Objectives: The objectives of the study are:

- a.) Assessing our recruitment capability
- b.) Evaluation of Data Collection Procedures and Outcome Measures
- c.) Assessing acceptability of intervention and study procedures
- d.) Evaluation of resources and ability to manage the Study and Intervention
- e.) Effectiveness of intervention

Long-Term Objectives

We are optimistic that renal denervation (RDN) will reduce self-reported pain in patients diagnosed with LPHS and that an adequately-powered randomised control trial (RCT) is feasible. We hope that RDN will eventually be considered a mainstream treatment for patients with LPHS.

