Our primary clinical hypothesis or **secondary outcome** is expected as a 30% reduction in subjective pain ratings using a 79-point (0-78) Mc Gill pain score and the Brief Pain Inventory Score in LPHS patients as compared to sham treated patients, at 6 weeks post treatment, which will be maintained at 3 and 6 months post-procedure.

Background Information

Loin Pain Hematuria Syndrome (LPHS) is a rare clinical disorder with a reported prevalence of 0.012% ¹ and typically impacts younger women. Since the initial description in 1963 ², it remains a poorly understood clinical condition characterized by severe, unilateral or bilateral loin pain localized to the kidney but in the absence of identifiable urinary tract disease. Hematuria can be either microscopic or macroscopic, and the renal abnormalities responsible for both pain and hematuria are unexplained. ¹

It is likely that multiple as yet unrecognized stimuli are responsible for the agonizing and unrelenting pain. Nociceptive fibers are transmitted in afferent A δ and C fibers from the kidney, coursing through the periarterial nerves, ascending by way of renal and intermesenteric plexi to the lowest splanchnic nerve and passing via the dorsal roots of T11 through L1 to the spinothalamic tracts. ^{2,3} The predominant clinical feature of LPHS is intense unilateral or bilateral loin pain which may be intermittent or constant dull ache with intermittent exacerbations. While spontaneous disappearance of the pain has been reported, the natural history is of recurrent episodes of debilitating pain refractory to conventional pain medications. Six decades after its initial description, there is no consensus on validated diagnostic criteria or optimal treatment strategies for LPHS. The diagnosis continues to be one of exclusion.

Pain is experienced unilaterally or bilaterally along the flank (costovertebral angle) and may be described as a "deep pain" which is intensified by a "gentle punch" and must be recurrent for six months or more in order to meet diagnostic criteria. ⁶ Pain should also be sufficiently severe to prompt the patient's primary care physician or urologist to prescribe or consider narcotic therapy. For patients identified as presenting with LPHS, hematuria is defined as greater than five red blood cells (RBC)/high-power field (HPF). ⁶ If there is a history of overt hematuria, it must be accompanied by

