- > Can we recruit appropriate participants?
- ➤ How difficult is a large-scale recruitment and retention for LPHS?
- ➤ Are the eligibility criteria appropriate?
- ➤ How many participants accept the eligibility criteria

2) Evaluation of Data Collection Procedures and Outcome Measures:

- ➤ How appropriate are the data collection procedures in this study?
- > Do participants have difficulty completing the measures proposed in this study?
- ➤ Does the overall data collection plan involve a reasonable amount of time, or does it create a burden for the participants?

3) Study Procedures:

- Are the study procedures acceptable to the participants?
- ➤ How many participants adhere to the study procedure?
- What is the acceptability of being in control group to the participants?
- ➤ Is the intervention suitable for and acceptable to the participants?
- ➤ How many participants will crossover to the intervention group after being in control group initially?
- ➤ What is probability of unexpected adverse events?

4) Evaluation of resources and ability to manage the Study and Intervention:

> Do we have enough resource and space to manage the study?

- Are the research investigator and staff capacities, expertise and availability for the planned research activities adequate?
- ➤ Evaluate the time to conduct each stage and aspect of the protocol? What are the time frames, and how do they coordinate with other responsibilities?

> Management of the ethics of the research:

- To what extent does staff comply with the approved protocol?
- How effectively are adverse events during implementation identified, documented, and reported?
- What happens if a participant experiences a clinical emergency?

Effectiveness of Intervention:

• Does the intervention show promise of being successful with the intended population?

Effectiveness of intervention will be determined based on following criteria:

- Whether participants receiving RDN have ≥ 30% reduction in pain medication dose (primarily opioids using morphine equivalent) as compared to sham treatment group at 3 and 6 months post-intervention, reported using a daily pain diary (attached).
- Whether participants receiving RDN have significant reduction in self-reported disability (Oswestry Disability Index) at 6 weeks, 3 and 6 months as compared to sham treatment group.

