- Whether participants receiving RDN (have significantly improved Quality of Life (EQ5D, SF-36 Questionnaire) at 6 weeks, 3 and 6 months as compared to sham treatment group.
- Whether participants receiving RDN have significantly improved mood (CES-D Short Form) at 6 weeks, 3 and 6 months as compared to sham treatment group.

Study Population:

This study will recruit 10 LPHS patients. Once a potential participant has been identified, the study will be explained for consideration. The potential participant will be given adequate time to carefully consider participation; this may include taking an unsigned copy home to discuss participation with family or friends before making a decision. If the subject agrees to participate, written informed consent will be obtained. Once a participant has consented to the trial they will undergo initial screening to ensure that they meet all of the eligibility criteria. The initial screening will be done on the basis of inclusion and exclusion criteria for participation in this study (except renal angiogram). The final step of screening process is a renal angiogram. LPHS patients who will meet all criteria after the initial screening period will undergo a renal artery angiogram to evaluate renal artery anatomy. Only subjects with eligible renal artery anatomy (between 3 mm and 8 mm) will be randomized. If the

renal angiogram shows that renal artery anatomy is not eligible for the study, participant will be excluded from the study.

Selection Criteria

Participants will be selected based on the following inclusion and exclusion criteria.

Inclusion/Exclusion Criteria

Inclusion criteria for participating in the study are:

- \geq 18 years of age
- Diagnosed with loin pain hematuria syndrome by a nephrologist, in consultation with a urologist.
- Current use of prescription pain medication for LPHS treatment.
- Arteries with a diameter between 3 mm and 8 mm.

Exclusion criteria for patients to be screened out of the study are:

- History of kidney auto transplantation
- Estimated glomerular filtration rate (eGFR) <45 mL/min/1.73m²
- Pregnant or nursing
- Need chronic oxygen support or mechanical ventilation via tracheostomy
 continuous positive airway pressure (CPAP) or bilevel positive airway pressure (BiPAP)
- Renovascular abnormalities
- Prior renal angioplasty, indwelling renal stents and/or aortic stent grafts
- Evidence of a somatoform disorder as per the SCID-5

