- Unavailable to travel to Regina, SK one day prior to the procedure to meet with the Principal Investigator and study coordinator

Trial Interventions

Renal angiography will be performed to confirm the suitability of renal artery anatomy for renal denervation therapy. If suitability criteria are met, the participant will then be randomized for a sham procedure or a renal denervation procedure by manager of the radiology suite, Regina using a computer program. Participants will be randomly allocated to one of two treatment arms: 1) renal denervation (treatment group) or 2) sham treatment (control group) immediately following the renal angiogram. All eligible participants will have an equal chance to be assigned to either treatment or control group with a 1:1 treatment allocation design being used. Participants will be given general anesthesia, thus they will be blinded to their randomised group assignment; they will not know the

difference between renal angiography procedure alone or renal angiography plus renal denervation procedure. After the procedure, the participants will be sent to the recovery room and the nursing team caring for the patient will be blinded to the procedure. The radiological aspect (sham or procedure) will not be entered on the hospital electronic medical rounds/ PACS. If the angiographic information is needed by other health care professional for a clinical event then it will be released upon request by the Interventional Radiologist.

Treatment Group: Participants remain blinded and are immediately treated with the renal denervation procedure.

Sham Group: Participants remain blinded and remain in the procedure table for at least 20 minutes prior to introducer sheath removal.

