EQ-5DTM: A descriptive questionnaire with 5 dimensions: mobility, self-care, usual activities, pain/discomfort and anxiety/depression. The dimensions have five levels (no, slight, moderate, severe and extreme problems). Participants select the level that corresponds to their perceived health status. Also, there is a vertical visual analogue scale (VAS) from 0 to 100, where participants record their health status lies with the end points being "The worst health you can imagine" and "The best health you can imagine". The VAS results may be used to quantify the patient's judgement on their own health.

McGill Pain Questionnaire (MPQ): A questionnaire to measure the quality and quantity of patient pain. The scale ranges from no pain (0) to maximum pain (78).

Brief Pain Inventory Questionnaire (BPS): A questionnaire to measure the severity and impact of pain on the patient's daily life and the perceived relief received from current intervention. The short form is has nine-points relating to patients occurrence of pain, areas of pain, rating pain at its worst in the last 24 hours, rating pain at its least in the last 24 hours, average pain level, current pain level, treatments being used, percentage of pain relief form medications used in the past 24 hours and specification of how pain has interfered with life.

CES-D: A questionnaire for measuring self-reported depression. Patients are asked to rate over the last week how often they experienced symptoms of depression. Scores range from 0 to 60, with higher score indicating more depression symptoms and lower scores indicating fewer symptoms.

Short Form Health Survey (SF-36): A health-related quality of life questionnaire that elicits information about participants using eight health concepts: physical functioning, role limitations due to physical problems, bodily pain, general health perceptions, vitality, social functioning, role limitations due to emotional problems and mental health. Scores range from 0 to 100, with lower scores relating to more disability and higher scores relating to less disability.

Oswestry Disability Index (ODI): A health questionnaire used to measure patient's functional disability. The questionnaire comprises of ten sections: pain intensity, personal care, lifting, walking, sitting, standing sleeping, sex life, social life and travelling. Index scores range from 0% to 100%, with higher scores relating to more disability and lower scores relating to less disability.

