Participants are allowed to withdraw from the study at any time without need to explain. Should the independent safety committee report patient safety concerns, the decision will be made as to whether the trial should be discontinued or whether the consent form must be modified to incorporate any new findings. Should new findings about the efficacy of this procedure for this indication emerge that would impact the premise for the study, the appropriateness of continuing the study will be reviewed. Should an emergency situation occur, the manager of the radiology suite who has access to the randomisation schedule will give the principal investigator the name, ID and treatment allocation of the participant involved in the emergency condition. The principal investigator will decide if there is an emergency with his experience as a physician. The research team has applied for

biomedical research ethics approval from the Regina Qu'Appelle Health Region (RQHR) Research Ethics Board

Statistics

Analysis for the feasibility trial will be restricted to qualitative thematic analysis and non-parametric analysis to compare the two small patient populations. No power or sample size calculations will be reported as this is not necessary for the feasibility phase of this trial.

Study Timeline

Study will commence only after getting approval from Health Canada. This study has been reviewed by Research Ethics Board, Regina and given provisional approval subject to the submission of No Objection letter from Health Canada.

The estimated duration of the study is 18 months. We plan to recruit patients in summer/fall 2018, with the treatment and control procedures conducted in the winter of 2018. This study involves a follow-up of six months from baseline. After this point, participants in the control group will go for the renal denervation treatment and will be followed for six month post procedure. Analysis and knowledge translation activities will occur after all follow-up are done. Please see the attached study scheme and timeline in Appendices folder.

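### Effectiveness is to be decided by an unranked list that omits pain, the primary clinical hypothesis, and does not say whether one or all of its criteria must be met

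*Protocol*

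**What the plan says.** The study hypothesis (Protocol, Overview) is feasibility and acceptability. Effectiveness is the last of five objectives, (e).

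Long-Term Objectives states a primary clinical hypothesis, also called the secondary outcome. It "is expected as a 30% reduction in subjective pain ratings using a" McGill scale of 0 to 78. The same sentence brings in the BPI and the timing: "and the Brief Pain Inventory Score in LPHS patients as compared to sham treated patients, at 6 weeks post treatment, which will be maintained". The maintenance visits are those at 3 and 6 months. Pain is therefore put first among the clinical outcomes, sham is the comparator, 6 weeks is the anchor, and the later visits are about maintenance.

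Measures gives the McGill one score, 0 to 78. It describes the BPI short form as nine areas, among them worst and least pain, "average pain level, current pain level, treatments being used", relief and interference. It gives no total and picks no item.

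Under Study Objective, Effectiveness of Intervention, the question is whether the intervention shows promise. The answer is then given a rule: "Effectiveness of intervention will be determined based on following criteria". Four criteria follow:

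- at least 30% lower pain medication dose than sham, at 3 and 6 months;
- significantly lower ODI at three visits;
- "significantly improved Quality of Life (EQ5D, SF-36 Questionnaire) at 6 weeks, 3 and 6 months as compared to sham treatment group";
- significantly better CES-D at three visits.

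No pain score is on the list. Statistics provides for qualitative thematic analysis and "non-parametric analysis to compare the two small patient populations".

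**The concern.** Two parts of the same document answer the effectiveness question differently. One makes pain the primary clinical hypothesis; the other says effectiveness will be determined by criteria that do not include pain. If pain improves and the listed scales do not, or the reverse, the Protocol does not say what the conclusion is.

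Within the list, the standard is statistical significance against sham on several instruments at three visits, with no statement of whether one result suffices or all are needed. On the first reading, chance alone will often supply a favourable result. On the second, almost nothing could qualify with 10 patients.

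Within the pain hypothesis, the McGill and the BPI may disagree, and the BPI score could be any of several numbers.

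At stake are the answer to objective (e) and the endpoint carried forward to the main trial, for which this study is meant to give direction.

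**Working it through.** The Protocol states no alpha, power or sample-size figure, so there is nothing of its own to reproduce.

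**Inputs from the Protocol.** "This study will enrol 10 LPHS patients" (Overview), "with a 1:1 treatment allocation design being used" (Trial Interventions), hence about 5 v 5. Visits at 6 weeks, 3 and 6 months. SF-36 with eight concepts; EQ-5D with a descriptive part and a VAS (Measures). Non-parametric two-group comparison (Statistics).

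**Assumptions, not in the Protocol.** Exactly 5 per arm with no dropout; exact two-sided rank-sum test at nominal 0.05; equal correlation between all contrasts, 0.5 as the central case and 0.3 to 0.8 as the range.

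**Step 1: count the contrasts.**

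- Significance criteria, one score per instrument: ODI, EQ5D, SF-36, CES-D = 4 × 3 visits = 12.
- Significance criteria, all scores: ODI 1 + EQ-5D 2 + SF-36 8 + CES-D 1 = 12 scores × 3 visits = 36.
- Medication dose adds 2 (3 and 6 months), giving 14 to 38 for the whole list. Dose has a 30% threshold instead of a significance standard, so the error rates below use 12 and 36.

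**Step 2: one named contrast.** There are 252 ways to split 10 ranks 5 v 5. The numbers of splits with U = 0, 1, 2, 3 are 1, 1, 2, 3. The two-sided p at U = 2 is 2 × 4/252 = 0.032, and at U = 3 it is 2 × 7/252 = 0.056. The test therefore rejects at U ≤ 2 in either direction. Attained error is 3.2% two-sided, and 4/252 = 1.6% in favour of RDN.

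**Step 3: at least one of K favours RDN, no true effect.** If the contrasts were independent, the chance would be 1 − (1 − 0.0159)^K, which is 17.5% for K = 12 and 43.8% for K = 36. They are correlated, so this is an upper benchmark. Simulated equicorrelated normal outcomes give:

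| Correlation | K = 12 | K = 36 |
|---|---|---|
| 0.3 | 15% | 31-32% |
| 0.5 | 12% | 24% |
| 0.8 | 8% | 12% |

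Simulation runs differ by about one percentage point. Counting significant results in either direction, the figures at correlation 0.5 are about 25% and 46%. The favourable-only figures are the relevant ones, because a result favouring sham cannot support a claim of effectiveness. At 14 and 38 contrasts, if dose were also tested this way, they are about 14% and 24%.

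**Step 4: the opposite rule.** If every contrast had to favour RDN significantly, the chance under no effect is practically zero for both K = 12 and K = 36. The two rules compatible with the text are thus far apart.

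**Step 5: the two pain scales.** Assume a true effect of 1 SD on each of two contrasts (McGill and one BPI score at one visit) and correlation 0.6. Each alone significantly favours RDN in about 21% of trials, and exactly one of the two does so in about 24%. Without a rank between them, that disagreement has no stated resolution.

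**The case against.** **The Protocol does have a lead outcome.** This stands in large part. A reader might infer that no lead is named at all, but Long-Term Objectives puts pain first, anchors it at 6 weeks and treats later visits as maintenance. What remains open is McGill against BPI, which BPI score, and whether the 30% is a between-arm difference in percent change or a responder definition. (Progress and clinical experience reports the earlier cohort as patients with more than 30% reduction.) The list that omits pain also remains unreconciled with it.

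**The pain hypothesis is not an any-of-six rule.** This stands. One might count six pain contrasts and note that, with an assumed SD of 40 points and correlation 0.5, at least one shows a 30-point advantage by chance in 36% of trials. The text joins the scales by *and* and requires maintenance; on that reading the chance is under 1%. The 36% is not a property of the plan.

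**This is detail for a statistical analysis plan.** Partly right. Alpha, testing order and scoring may sit in an unseen plan. A reader might also infer that the deciding contrast would be chosen after allocation is known, since analysis follows unblinding; an unseen plan could fix it earlier, so the Protocol does not show that. But the Protocol itself states what will determine effectiveness and by what standard, and that rule is indeterminate and at odds with its own hypothesis.

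**It is a feasibility trial.** This limits the consequence. No power is claimed, and evaluating several outcome measures is a stated objective, so carrying many instruments is not a fault. Letting any of them decide effectiveness is.

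**Conclusion.** The concern holds in a limited form. Two parts of the Protocol need reconciling: the primary clinical hypothesis is pain at 6 weeks, yet the list said to determine effectiveness leaves pain out. That list does not say whether one or all criteria must be met, and the BPI has neither a rank against the McGill nor a defined score.

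If one favourable significant result were enough, the chance of it under no effect is about 12% to 24% at correlation 0.5, and 8% to 32% over correlations 0.3 to 0.8, against 1.6% for one named contrast. These figures rest on the assumed alpha, test, 5 v 5 split and correlations. The upper end also requires every SF-36 scale and the EQ-5D VAS to count separately, which the Protocol neither states nor rules out.

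A reader might go further and say that the same data could support opposite conclusions. The documents support only that effectiveness could be declared shown or not shown, not benefit against harm. The feasibility conclusions are untouched; the effect is confined to objective (e) and the endpoint passed to the main trial.

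**What to change.** - Reconcile Long-Term Objectives with the Effectiveness of Intervention list so that objective (e) rests on one lead clinical contrast. McGill total (0-78) at 6 weeks against sham is one natural choice: it is the first scale and visit the hypothesis names, and the scale used in the earlier 12-patient cohort.
- State whether the 30% target is a between-arm difference in percent change or a responder definition.
- State that the 3- and 6-month McGill contrasts describe maintenance.
- Name one BPI score as supportive, and say that a disagreement with the McGill is reported and does not override it.
- Label medication dose, ODI, EQ5D, SF-36 and CES-D exploratory, with one named score each and all visits reported as estimates with intervals. State that no effectiveness claim rests on any single significant result.

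The cost is a few sentences, with no added patients, visits or data. The downside is that a favourable result on a secondary scale or visit can no longer be presented as showing effectiveness.

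### Three of the four effectiveness criteria ask for significant differences from sham in an unpowered trial of 10 patients whose question is whether the treatment shows promise

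*Protocol*

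**What the plan says.** The protocol's Study Objective section, under Effectiveness of Intervention, poses this question: "Does the intervention show promise of being successful with the intended population". It continues: "Effectiveness of intervention will be determined based on following criteria". Four bullets follow.

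- **Pain medication:** a reduction of at least 30% relative to sham at 3 and 6 months. This is a magnitude.
- **Disability:** whether RDN participants "have significant reduction in self-reported disability (Oswestry Disability Index) at 6 weeks, 3 and 6 months as compared to sham treatment group".
- **Quality of life:** whether they "have significantly improved Quality of Life (EQ5D, SF-36 Questionnaire) at 6 weeks, 3 and 6 months as compared to sham treatment group".
- **Mood:** whether they "have significantly improved mood (CES-D Short Form) at 6 weeks, 3 and 6 months as compared to sham treatment group".

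On size, Study Population says "This study will recruit 10 LPHS patients", and Trial Interventions describes randomisation "with a 1:1 treatment allocation design being used". The Statistics section restricts the analysis to thematic and non-parametric methods and declines a power calculation as unnecessary at this phase. The two Overview sections connect the assessment of statistical and clinical significance with a larger trial. Separately, Long-Term Objectives states a pain hypothesis: a 30% reduction "in LPHS patients as compared to sham treated patients, at 6 weeks post treatment, which will be maintained at 3 and 6 months post-procedure".

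**The concern.** Promise and statistical significance are different standards. In a very small trial, a treatment can show a large and consistent advantage and still fail a significance test. Three of the four bullets nonetheless make significance against sham the measure of effectiveness. Nothing in the protocol labels those comparisons descriptive or exploratory.

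Two things could go wrong in the report. A real benefit on disability, quality of life or mood could be recorded as absent, or an isolated chance result could be presented as effectiveness. Which risk dominates depends on how the comparisons are combined, and the protocol does not say. Either could mislead those designing the main trial.

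**Working it through.** The protocol gives no alpha, test, effect size or SD for these scales, so it has no figure to reproduce. What follows are operating characteristics under stated assumptions.

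**From the protocol.** N = 10, allocated 1:1, so about 5 v 5. The comparison is non-parametric. Four instruments (ODI, EQ5D, SF-36, CES-D) at three visits give 4 × 3 = 12 comparisons. This is a minimum, because EQ5D and SF-36 each yield more than one score.

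**Assumed.** Exact two-sided rank-sum test at 0.05; normal data with a shift of 1, 1.5 or 2 SD; correlations between scales and between visits of 0.3/0.5, 0.5/0.7 and 0.8/0.8.

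**Step 1: what one test needs.** U counts the 5 × 5 = 25 RDN–sham patient pairs that favour RDN. There are C(10,5) = 252 equally likely splits under the null. The numbers of splits with U = 0, 1, 2, 3 are 1, 1, 2, 3.
- Rejecting at U ≤ 2 or U ≥ 23: 2 × (1+1+2)/252 = 8/252 = 0.032.
- Adding U = 3 and U = 22: 2 × 7/252 = 0.056, which exceeds 0.05.

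So a significant result for RDN needs at least 23 of 25 pairs in its favour.

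**Step 2: power for one scale at one visit (simulated).**

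| Arms analysed | 1 SD | 1.5 SD | 2 SD |
|---|---|---|---|
| 5 v 5 | 21% | 43% | 68% |
| 5 v 4 (one lost) | 18% | 37% | 60% |
| 4 v 4 (one lost per arm) | 14% | 29% | 49% |
| 4 v 6 (uneven randomisation) | 22% | 45% | 69% |

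At 5 v 5 the miss rate is 100 − 21 = 79% at 1 SD and 100 − 43 = 57% at 1.5 SD. Power of 80% needs about 2.3 SD.

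**Step 3: the two possible decision rules (5 v 5, simulated; ranges run over the assumed correlations).**

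| Rule | No true effect | Every scale truly better by 1 SD |
|---|---|---|
| A scale counts only if significant at all three visits | Any scale qualifies by chance: below 1% | A given scale qualifies: about 4–8% |
| Any one of the 12 suffices | At least one result favouring RDN: about 9–15% | At least one result favouring RDN: 57–83% |

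The first rule is the literal reading of the bullets: it nearly removes chance findings but misses almost every real 1 SD effect on a scale. The second misses less but admits chance findings. Bonferroni cannot rescue the second rule: the smallest attainable p is 2/252 = 0.0079, above 0.05/12 = 0.0042.

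**Step 4: precision if estimation replaces testing (5 v 5, Hodges–Lehmann).**
- 3rd to 23rd ordered difference: level 1 − 8/252 = 96.8%, median width about 3.25 SD.
- 5th to 21st: level 1 − 2 × (1+1+2+3+5)/252 = 1 − 24/252 = 90.5%, median width about 2.35 SD.

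**The case against.** **The word is ambiguous.** The protocol names statistical and clinical significance separately, and its neighbouring criteria are 30% magnitudes. *Significant* might therefore mean a meaningful change, and then the power figures fall away. This stands as a limit. The statistical reading remains the natural one, because these bullets compare with sham and, unlike the medication bullet, give no magnitude. On the other reading the criterion has no threshold at all, and the rewording still helps.

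**An SAP may settle it.** The test, alpha and multiplicity rule are commonly left to an SAP, which is not at hand, and their absence is not criticised here. Nor is the absence of a power calculation, which is acceptable in a feasibility trial. What the protocol itself fixes is significance as the criterion, and naming a test would not make that suitable at 5 v 5.

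**The two harms do not occur together.** A reader might infer that the trial is both likely to miss promise and likely to produce a chance finding. Step 3 shows that these belong to different rules. If any one of 12 suffices and every scale improves by 1 SD, at least one favourable result appears in 57–83% of trials, so promise is not usually missed overall.

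**Effects may be large.** At 2 SD a single comparison succeeds more often than not. The protocol's earlier figures, however, are pain responders in an uncontrolled 12-patient cohort, for which it concedes a possible placebo effect. It gives no sham-controlled effect for these four scales.

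**An interval is the same test in another form.** The 96.8% interval excludes zero exactly when the rank-sum test rejects. This stands, so the fix must also say that promise is not judged on whether an interval excludes zero.

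**Conclusion.** The point holds as a minor one. Three of the four criteria use an undefined significance standard that suits neither the sample size nor the question of promise. Under the assumed test, level and 5 v 5 split, a true benefit of 1 to 1.5 SD on one scale at one visit is missed about 79% to 57% of the time. The figures across comparisons depend on assumed correlations and on a decision rule that the protocol leaves open.

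Two stronger readings are not supported. A reader might infer that effectiveness as a whole is defined by significance, or that promise is the trial's only interest in efficacy. The medication bullet is a magnitude, effectiveness is listed as an objective in its own right, and there is a separate pain hypothesis. A reader might also infer that the decision to run the main trial depends on these tests. The Study Hypothesis ties that decision to feasibility and acceptability, so the consequence is confined to how effectiveness is reported.

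**What to change.** In Effectiveness of Intervention:

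1. Replace the lead-in sentence with: *Promise of effectiveness will be described using the following.*
2. Leave the medication bullet as it is. Reword the other three as: *The estimated RDN–sham difference in [ODI / EQ5D and SF-36 / CES-D] at 6 weeks, 3 and 6 months, with an exact non-parametric (Hodges–Lehmann) confidence interval.*
3. Add one sentence: *These comparisons are exploratory; promise is judged on the size and direction of the estimates, not on p-values or on whether an interval excludes zero, and is read alongside the pain hypothesis.*

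This stays within the non-parametric analysis already planned and needs no new data. The cost is that no significance claim can be made for these scales and that the intervals will be wide: a median of about 3.25 SD at the 96.8% level, or 2.35 SD at the 90.5% level, with 5 v 5. That width is a fair picture of what 10 patients can show.
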